Although exercise is known to delay cognitive decline and decrease our risk of Alzheimer's disease, there is a lack of understanding of how exercise protects the aging brain. The overall goal of this study is to determine the effects of moderate intensity physical exercise training on relational learning processes and functional brain connectivity in healthy older adults. We examine the effect of moderate intensity exercise training on learning and connectivity with a 6-month randomized controlled trial (RCT) that compares moderate intensity stationary cycling to very light intensity cycling. We further test the mechanisms involved by determining the selective acute effects of moderate intensity exercise that would improve cardiorespiratory fitness compared to light intensity exercise, and by determining if change in cardiorespiratory fitness is a key factor for benefits on functional connectivity and learning.

5. Background and Specific Aims

Animal models robustly support that endurance exercise protects brain areas vulnerable to aging such as the hippocampus (1) and that these benefits are directly related to better *learning* (1-3). In contrast, human studies have shown mixed findings on the cognitive benefits of exercise with healthy older adults (4-9), even when the studies are well-powered and exercise benefits brain regions that deteriorate with aging including the hippocampus and prefrontal cortex (10-15). Given the importance of cognition for independence in daily life, this presents a critical need to determine how exercise works against the mechanisms driving *cognitive aging* (16, 17). Our **objective** with the EXTEND trial is to fill this translational gap by determining if exercise improves the same kinds of learning in older adults that have been shown to improve in animal models from exercise by improving hippocampal function. ***Our overall hypothesis is that exercise improves learning when it increases functional hippocampal-cortical communication that otherwise declines with aging.*** We test this hypothesis with 3 aims:

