- 1. Determine the relationship between chronic training-related effects of moderate intensity exercise on hippocampal-cortical functional connectivity (FC) and changes in learning from exercise.** Although we have shown that long-term moderate intensity exercise training improves hippocampal-cortical FC, it is unclear how these changes from exercise counteract cognitive aging. Our *hypothesis* is that training-related changes in hippocampal-cortical FC with the Default Network (DN) will improve learning in an array of tasks that require the hippocampus for acquisition of new relational memories, but not in tasks that do not require the hippocampus to learn such as motor or response learning. We test this with a 6-month RCT that compares the effects of moderate vs very light intensity exercise of the same modality (stationary cycling) on learning.
- 2. Determine the relationship between rapid transient effects of a single session of moderate intensity exercise on hippocampal-cortical FC and training-related changes in hippocampal FC and learning from exercise.** Animal studies have shown that exercise rapidly affects hippocampal plasticity following a single exercise session, that effects last up to 1 hour, and occur in the same pathways that benefit from long-term training. These effects

[figure not shown]
may reveal insight about the mechanisms of change from training. Our preliminary data support the *hypothesis* that we can see such rapid effects in humans with fMRI. We test this by assessing acute increases in functional hippocampal-cortical *FC* that are specific to moderate intensity exercise, and determining if this response predicts improvements in hippocampal *FC* and learning from 6 months of exercise training.

3. Determine how moderate intensity exercise changes hippocampal-cortical *FC* and learning. Our data indicate that cardiorespiratory fitness (CRF) is a critical factor in cross-sectional differences of hippocampal-cortical *FC* and learning. CRF reflects complex improvements in vascular, cardiac, and metabolic health from moderate intensity exercise. Given the observed rapid effects, our working *hypothesis* is that the physiological processes leading to improved CRF from moderate intensity exercise are critical to the benefits on hippocampal *FC* and learning. We test this by assessing whether individual differences in training-related changes hippocampal-cortical *FC* and learning are predicted by training-related changes in CRF.

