Data from this trial will be *significant* by revealing mechanisms by which exercise could mitigate age-related cognitive decline in learning that depends on the hippocampus. There currently are no treatments that reliably reverse the course of cognitive aging associated with hippocampal deterioration. Exercise has shown promise in animal studies, but this promise has not been successfully translated to human studies of healthy aging. Data from this study could help bridge this gap. Given the hippocampus is central to Alzheimer's and related dementias, results could also lead to an understanding of the mechanisms by which exercise reduces risk of this devastating and costly disease (18-20).

6. General Study Design

The study is a standard randomized, controlled trial, single-blind design of relatively inactive but healthy older adults. A target N of 120 participants will participate and be randomized to either an experimental (moderate intensity) treatment group (N=60) or an active control (light-intensity + stretching) group (N=60). Since we are interested in the effects of exercise training on cardiorespiratory fitness and in turn cognitive performance, we will ask participants to complete assessments of cardiorespiratory fitness (CRF) and cognition before and after the training program. Following completion of pre-training screening, fitness, and cognition assessments, participants will be randomly assigned into one of two groups indicating order of acute exercise conditions and will again be randomized to determine their chronic training group (see Figure 1). Including pre- and post-training testing, participants who complete the study will be enrolled for approximately 28-30 weeks (~4 weeks pre-testing, 24 weeks training, and ~2 weeks post-testing).

Study Flow Chart:

Figure 1. Overall study timeline. Note randomization occurs once for counter-balancing the order of acute phase conditions, and then again for assignment to intervention group.

*MRI denotes that the first MRI of the first acute exercise visit will serve as the pre-test MRI for the first acute visit, and as the pre-test MRI for the 6-month training study.

7. Study Population

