Following the acute exercise session, participants will continue to the second phase by entering one of two training groups, as determined by their initial randomization:

- **Moderate intensity exercise training** will be a 24-week supervised cycling program, with supervision directly from our research team. Participants will start in waves of ~5 per wave. All participants will first receive a one-on-one orientation with an exercise training specialist that has been trained by [name] in monitoring an exercise program for healthy older adults. Since participants will initially be relatively inactive, the exercise group will start with a 5 minute-warm-up, 20-minutes moderate intensity cycling at 50-60% Heart Rate Reserve (HHR) and 20 minutes passive cycling, and 5 minute cool-down per session, for 3 sessions/week. In each additional week, we will replace 5 minutes of passive cycling with 5 minutes of moderate intensity cycling per session, until the total time for moderate intensity is 40 minutes per session by the start of week 5 (with additional 5 minute warm-up and 5 minute cool-down). Starting at week 6 the exercise group will increase their moderate intensity cycling to 60-70% HHR with a similar build up to the first 5 weeks. Starting at week 13 the exercise group will increase their moderate intensity cycling to 70-80% HHR with a similar build up to the first 5 weeks. This program allows for a gradual build-up of endurance while including training for approximately 135 minutes of moderate-to-vigorous intensity exercise per week.
- **Functional fitness training** will be a 24-week supervised exercise program designed to focus on functional flexibility and mobility, with supervision directly from our research team. All participants will first receive a one-on-one orientation with an exercise training specialist that has been trained by [name] in monitoring an exercise program for healthy older adults. Training will start with a 15 minute-warm-up of stretching, 20 minutes of light intensity cycling and 15 minutes of dynamic stretching to increase range of motion and functional fitness, for 3 sessions/week. In each additional week, additional stretches will be added to maintain variety and improve flexibility of all major muscle groups. Our goal is to maintain HR at or below 40% HRR during training sessions for this group.

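### Aim 1 says the 6-month trial varies intensity within one modality, but control sessions start at 30 of 50 minutes stretching, so the group difference cannot be credited to intensity alone

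*Protocol*

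**What the plan says.** Two parts of the Protocol describe the 6-month contrast as intensity within cycling. Aim 1 in section 5 says the trial "compares the effects of moderate vs very light intensity exercise of the same modality (stationary cycling) on learning". The summary before section 5 says it "compares moderate intensity stationary cycling to very light intensity cycling".

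Two other parts describe the control differently. Section 6 calls it an "active control (light-intensity + stretching) group". Section 15 titles it functional fitness training, gives it a flexibility and mobility focus, and sets out the session: "Training will start with a 15 minute-warm-up of stretching, 20 minutes of light intensity cycling and 15 minutes of dynamic stretching". The progression it states is this: "In each additional week, additional stretches will be added to maintain variety and improve flexibility of all major muscle groups". The heart-rate target is also stated: "Our goal is to maintain HR at or below 40% HRR during training sessions for this group".

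For the moderate arm, section 15 prescribes a starting block of "20-minutes moderate intensity cycling at 50-60% Heart Rate Reserve (HHR) and 20 minutes passive cycling", with a short warm-up and cool-down around it. Passive minutes are then replaced by moderate ones until moderate cycling fills "40 minutes per session by the start of week 5 (with additional 5 minute warm-up and 5 minute cool-down"). No stretching is mentioned for this arm.

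Section 17 of the Protocol and of the SAP labels the chronic groups by intensity alone (M and L). It fits one group indicator with sex and age, and plans a similar model for learning rate. The SAP does not mention stretching.

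**The concern.** Holding modality constant is a specific design property, and it carries a specific inference: if the arms differ on connectivity or learning, intensity is the reason, because the activity was otherwise the same. Aim 1 claims that property for the 6-month trial. The control in section 15 spends more than half of its starting session off the bike, so the property is absent.

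What is at stake is interpretation. A positive result could reflect higher intensity, more time cycling, less stretching, or some combination. A null result is equally hard to read: it could mean that intensity does not matter, or that stretching had an effect of its own that narrowed the gap. A reader of the SAP alone, who sees only M and L, would take the contrast to be intensity and nothing else.

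**Working it through.** The plan gives no figure of its own for this contrast, so there is nothing to reproduce. The check adds up the session components in Protocol section 15. All minutes are prescribed, not achieved, and both arms are prescribed 3 sessions per week.

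**Control, starting session**
- Total: 15 + 20 + 15 = 50 min.
- Stretching: 15 + 15 = 30 min; 30/50 = 60%.
- Light cycling: 20 min; 20/50 = 40%.
- Per week: stretching 30 × 3 = 90 min; cycling 20 × 3 = 60 min.

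**Moderate arm, starting session**
- Total: 5 + 20 + 20 + 5 = 50 min.
- Cycling block: 20 moderate + 20 passive = 40 min; 40/50 = 80%.
- Warm-up and cool-down: 5 + 5 = 10 min, content not stated. If done on the bike, cycling is 50 min; if not, 40 min.
- Per week: cycling 40 × 3 = 120 min, or 50 × 3 = 150 min if the warm-up and cool-down are cycling.
- By week 5 the block is 40 moderate + 0 passive, still 40 min. The initial build-up changes the intensity mix, not the length of the block.

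**Difference at the start**
- Session length: 50 versus 50 min, equal.
- Cycling: at least 40 versus 20 min per session, and at least 120 versus 60 min per week.
- Stretching: 30 min in the control against 0 to 10 min in the moderate arm, the upper end applying only if all of the unstated warm-up and cool-down is stretching. The difference is 30 − 10 = 20 to 30 − 0 = 30 min per session, or 60 to 90 min per week.
- Intensity: control at or below 40% heart-rate reserve; moderate block starting at 50–60%.

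**What the planned analyses can separate**
- *Primary and learning models.* There are two arms and one group indicator. Intensity, cycling time and stretching all switch with that indicator, so one coefficient carries all three. Sex and age do not help to separate them.
- *Mediation through change in cardiorespiratory fitness (section 17).* Change in fitness is not randomised, and the model has no term for cycling minutes or stretching.
- *Percent of sessions in the prescribed heart-rate zone (section 17, adherence).* Within an arm the prescribed programme is the same for everyone, but adherence to the zone is not randomised and the analysis is labelled exploratory.

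No planned randomised analysis isolates intensity.

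**The case against.** The strongest reply is that this is a drafting lapse which the Protocol itself discloses. Section 6 names the stretching component and section 15 gives its minutes, so nobody running the trial would be misled. Section 17 tests only whether the groups differ and does not say that intensity is the sole difference. The control's heart-rate ceiling covers the whole training session, stretching included, so a session-level intensity contrast survives. Stretching may be an inert filler that equalises contact time.

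Much of this stands. The stretching is disclosed, the intensity contrast is real, starting session length and frequency match, and the stated null hypothesis is sound.

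Two parts do not. Disclosure elsewhere does not repair Aim 1, because the aim defines the claim to be made and the analysis text follows it with intensity-only labels. And the documents offer no evidence that stretching is inert. If it were, starting cycling time would still differ at least two-fold, and the same-modality description would still be wrong for a session that is 60% stretching.

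A reader might also infer more than the text supports:
- *That the randomised comparison is biased.* It is not. Assignment is random for the analysed participants, and the coefficient estimates the programme difference.
- *That the two-fold cycling difference holds for all 24 weeks.* Later control minutes are not given, so no 24-week total can be stated.
- *That the weekly figure of about 135 minutes in section 15 gives a cycling ratio.* It is described as moderate-to-vigorous exercise, not as cycling time. Nor are minutes at each arm's own target usefully compared: the targets differ, and the moderate build-up recurs from weeks 6 and 13.
- *That the acute cross-over has the same fault.* Both of its conditions are 20 minutes of stationary cycling at the same pedalling speed, so this point does not reach it.

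**Conclusion.** Wrong as written, with modest weight. Aim 1 and the summary credit the 6-month trial with a property that sections 6 and 15 show it lacks.

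The supportable size is the starting prescription worked out above: at least twice the cycling time in the moderate arm, and 60% of the control session spent stretching. The lower bound of 40 minutes rests on the stated cycling block alone and needs no assumption about the warm-up and cool-down.

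How much this matters for the estimate is unknown. The documents give no figure for the effect of stretching, or of light-cycling time, on connectivity or learning. It may be negligible. The plan cannot show that it is, so the chronic results support a statement about two programmes and not about intensity alone.

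**What to change.** 1. Protocol section 5, Aim 1: delete the clause that says the arms share one modality.
2. Protocol summary and Aim 1: describe the contrast as a progressive moderate-to-vigorous cycling programme versus a programme of light cycling plus stretching.
3. Section 17 of the Protocol and of the SAP: add one sentence defining chronic M and L in those terms and stating that the group coefficient estimates the difference between the programmes. M and L can then stay as shorthand.
4. Limit conclusions on chronic connectivity and learning, positive or null, to the programme difference.

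The cost is a few sentences and a narrower claim: the chronic trial can no longer be presented as a test of intensity alone. The interventions, the model and the sample size stay as they are.

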- Spatial Navigation Task (version B) - delay phase - 10 minutes. Following a 30-minute delay (during which the task-switching and associative learning tasks are completed), participants will be asked to re-trace their route to a given landmark.
- Processing speed measures (Digit symbol substitution, pattern comparison, letter comparison)

13. Randomization

Randomization will occur once to determine the order of exercise conditions for the acute cross-over design, and again to determine the training groups (see Figure 1). Eligible participants will be randomized to one of two randomization groups that indicates the order of their acute exercise conditions, a separate randomization will occur to determine their exercise training group (see

Figure 1). Therefore, *all* enrolled participants complete an acute exercise assessment with both light and moderate intensity sessions (21). Following the acute exercise session, participants will continue in one of two training groups (moderate, light intensity).

When participants express interest to participate in their exercises as a couple (dyad), co-enrollment will be allowed on a limited basis. Co-enrollment means that only one of the dyad will be randomized and the partner will be automatically assigned to the same intervention group. The data for the partner then qualifies as “missing” for all analyses that depend on assumptions of random assignment. Our power analysis accounted for losing up to 15% of data due to drop out (10%) and scanner motion (5%), which would leave the sample at about 100 participants and still at strong power (~90%, two-tailed) with allowance for covariates. Based on our pilot study and adherence so far, we predict to lose less data from drop-out and motion than we initially predicted. Therefore, we will consider non-randomized partners as another source of “missing data” and set our limit for non-randomized dyads to N=6 (5%).

For participants who drop-out after randomization, we will take the following approach to determine the best type of post-testing to be done at the time of drop-out:

- First, ask them if they are still willing to do their post-test MRI and full cognitive testing sessions.
- If they cannot do all the testing, we will ask if they could do one 2-hour cognitive testing session in the lab. This would allow us to collect our learning and memory behavioral measures that tap into hippocampal function and our abbreviated battery including the RAVLT in-person.

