- However, if the drop-out participant is not willing to return to the lab for post-testing, then we will ask them if they are willing to do a brief phone survey which includes the tasks in the short battery above.

14. Neuroimaging measures

This study will utilize the 3T GE Discovery 750W MRI scanner to collect images that allow us to measure brain structure (T1, T2, diffusion), functional connectivity of brain networks sensitive to aging (resting state BOLD), neuronal metabolism (quantitative susceptibility mapping and T1ρ), and cerebrovascular reactivity (BOLD response during a breath hold paradigm). We expect to scan for one hour before each acute exercise session and 30 minutes following each acute exercise session, and for 1 hour following completion of the 6-month exercise training intervention (see outline below). In the event that a participant is uncomfortable in the scanner (e.g., wide shoulders or large head size), but would like to participate in scanning, we will prioritize T1 structural images and resting state fMRI scans which are central to testing our specific aims. Following each MRI session, images will be downloaded directly from XNAT into [BIDS](#) format. Quality control procedures will be conducted following data collection each week using [mriqc](#).

MRI scans acquired at first baseline MRI visit:

- Pre-exercise:
 - 3 x 8min resting state fMRI scans (eyes open)
 - Breath-hold task

- T1 weighted anatomical image (MPRAGE)
- T2 FLAIR anatomical image
- Post-exercise:
 - 3 x 8min resting state fMRI scans (eyes open)

MRI scans acquired at second baseline MRI visit:

- Pre-exercise:
 - 3 x 8min resting state fMRI scans (eyes open)
 - 64 Directional DTI scan to assess white matter integrity
 - T1 ρ
- Post-exercise:
 - 3 x 8min resting state fMRI scans (eyes open)

MRI scans acquired at post-training MRI visit:

- 3 x 8min resting state fMRI scans (eyes open)
- Breath-hold task
- T1 weighted anatomical image (MPRAGE)
- T2 FLAIR anatomical image
- 64 Directional DTI scan to assess white matter integrity
- T1 ρ

*Note the post-test MRI will begin in the mock MRI room with assessment of the RAVLT, oral trail-making, and the FAS word fluency tasks.

15. Research Interventions

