The interaction term allows the effect of the acute M – L difference to vary by chronic group. When $\gamma_3 \neq 0$, the acute difference has a different effect for the chronic M group. Therefore, the null hypothesis of interest for the second aim is $H_0: \gamma_3 = 0$. Missing data will again be handled with multiple imputation. The first test will consist of the same hippocampal-cortical outcome described above, and additional exploratory analysis will be performed adjusting for multiple testing.

The main analysis for all three aims will be conducted under the intent-to-treat (ITT) principle. A participant will be counted as a member of their group at the time of re-randomization in the chronic phase. Participants will be analyzed in their initial group assignments in a blinded manner, regardless of dropout or adherence. Fidelity will be assessed by separate regression models in which CRF is the outcome with the goal of examining if the treatment caused a sufficient difference in CRF. A small number of participants will be allowed to enroll as a couple with the couple being the unit for random assignment. One member of the couple will be randomly assigned for analysis and the other member's data will not be considered for analysis in the primary aim (data might be inspected for exploratory purposes).

Due to its importance in achieving our objectives, the power analysis is based on preliminary data for the relationship between aerobic exercise training change in learning rate on one of the learning tasks. Based on the effect size observed from a multiple linear regression of training group and additional covariates as predictors, our power analysis maintains an allowance of 10 predictor variables including training group. Based on these considerations, a sample size of 120 older adults, randomized to one of two training groups (N=60 per group), would ensure 95% power. If we further account for up to ~15% (N=18) missing data due to factors such as (a) motion or drop-out during scanning, (b) missing post-test due to drop-out during training, or (c) co-enrollment with spouse, we would still have a final sample size of ~N=100, which would achieve ~90% two-tailed power and still result in larger group sizes than our published results of hippocampal-cortical FC following exercise training. We do not have plans for formal interim analyses and there is no predefined interim statistical analysis or result that would cause termination of the trial.

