ECG ergometer stress test with VO2 monitoring: A physician with training in cardiology will be present for all pre- and post-intervention maximal exercise tests that are conducted at the Exercise Physiology Lab at the Field House. The physician will monitor the subject's 12 lead ECG, blood pressure, and any symptoms. American Heart Association/American College of Sports Medicine guidelines for contraindications to begin the test, and indications to stop the test will be followed. Our trained exercise specialist administers the exercise test, with supervision by a physician. [name] or [name] will supervise our pre- and post-intervention maximal exercise tests.

After the ECG Stress/VO2 test, participants will be monitored for 15 minutes to ensure they are symptom free and that the ECG is back to baseline before the participant is released. Personnel involved in exercise testing will be required to be certified in CPR and First Aid. In addition, the EPL is equipped with an AED, phone to call 911, and a fully supplied crash cart maintained by the University of Iowa Hospitals and Clinics. The pre-intervention exercise test serves as a baseline measure of cardiorespiratory fitness as well as a screening tool to ensure no cardiovascular abnormalities are present during moderate-to-vigorous aerobic exercise.

Following this screening session, the physician's role is to indicate whether the participant is now eligible to continue with participation in an exercise training program with minimal risk of an adverse event. Participants with evidence of cardiovascular disease at baseline (e.g., evidence of myocardial infarction, abnormal cardiac arrhythmia, myocardial ischemia, conduction delays) or during the exercise test (>1 mm ST segment depression or elevation; >3 beat ventricular tachycardia; atrial fibrillation, chest pain suggestive of angina) will be excluded from the study because of the associated increase in risk for an adverse event during training.

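### No step of the drop-out procedure requests the post-training fitness test, and no missing-data method is stated for the fitness (CRF) analyses that depend on it

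*Protocol*

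**What the plan says.** Protocol section 13 sets the post-testing requests for anyone who drops out after randomization. The steps are:

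1. "First, ask them if they are still willing to do their post-test MRI and full cognitive testing sessions"
2. "If they cannot do all the testing, we will ask if they could do one 2-hour cognitive testing session in the lab"
3. For those unwilling to return to the lab, "we will ask them if they are willing to do a brief phone survey which includes the tasks in the short battery above"

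The aim of these steps is to "determine the best type of post-testing to be done at the time of drop-out". None of them names the maximal exercise test.

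Elsewhere CRF is a planned pre- and post-training measure. Section 6 says participants will be asked for "assessments of cardiorespiratory fitness (CRF) and cognition before and after the training program", and section 18 says "A physician with training in cardiology will be present for all pre- and post-intervention maximal exercise tests".

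Section 17 of the Protocol, repeated in the SAP, uses CRF in two places. One is the fidelity check: "Fidelity will be assessed by separate regression models in which CRF is the outcome". The other is the Aim 3 mediation, where change in CRF is the mediator and which is labelled a secondary analysis. The same section states: "The main analysis for all three aims will be conducted under the intent-to-treat (ITT) principle". It adds that participants stay in their assigned group whatever their drop-out or adherence.

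Multiple imputation is specified for the primary model and again for Aim 2. The pattern-mixture sensitivity analysis appears in the paragraph on missing data, which is written about the primary analysis. Neither document says how missing CRF is handled in the fidelity or mediation models.

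**The concern.** A site that follows section 13 as written can obtain connectivity and learning data from a willing drop-out, but it is never prompted to obtain CRF. CRF would then tend to be missing for people who stopped the training that was meant to change it, where the value is most informative.

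Two results depend on this. The CRF difference between arms is the trial's evidence that the two programmes differed in the intended way. Change in CRF is also the explanatory variable in Aim 3. If drop-outs have no observed CRF and the analyst uses completers, or imputes from arm and baseline alone, the estimate describes those who kept training rather than those randomized. In Aim 3, a drop-out's observed connectivity and learning could also be paired with a CRF value predicted from people who continued. A CRF value that was not measured at post-test cannot be recovered later.

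**Working it through.** **The plan's own loss figures.** Sections 13 and 17 allow for about 15% loss from 120: 0.15 × 120 = 18, leaving 102, which agrees with the stated figure of about 100. No effect size or alpha is given. Assuming a two-sided alpha of 0.05 and solving for the effect that gives 95% power at N = 120 with 10 predictors (f² = 0.110), power is 91.3% at N = 102 and 90.7% at N = 100. This agrees with the stated figure of about 90%, but it is only a consistency check. Section 13 splits the 15% into 10% drop-out and 5% scanner motion. Motion does not remove CRF, so the relevant rate is 10%: 0.10 × 120 = 12 people, or 6 per arm if drop-out is equal.

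**Formula.** Let D be the CRF contrast between arms in completers, p the drop-out proportion in the moderate arm, and r the share of the CRF gain that moderate-arm drop-outs keep. Assume no CRF change in the light arm, for completers and drop-outs alike.

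- Intent-to-treat contrast = (1 − p)D + p·r·D
- Overstatement by the completer contrast = 1 / (1 − p + p·r) − 1

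**Results with 12 drop-outs in total** (p and r are scenarios; the documents give neither by arm):

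| Drop-outs, moderate / light | p | r = 1 | r = 0.5 | r = 0 |
|---|---|---|---|---|
| 6 / 6 | 0.10 | 0% | 1/0.95 − 1 = 5.3% | 1/0.90 − 1 = 11.1% |
| 9 / 3 | 0.15 | 0% | 1/0.925 − 1 = 8.1% | 1/0.85 − 1 = 17.6% |
| 12 / 0 | 0.20 | 0% | 1/0.90 − 1 = 11.1% | 1/0.80 − 1 = 25.0% |

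**Does multiple imputation repair this?** This was simulated with 60 per arm, an assumed completer effect of 0.60 SD, an assumed baseline correlation of 0.8, 20 imputations and 1,500 runs. The imputation model held arm and baseline CRF only.

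| Scenario | Full-data ITT | Completers | Imputed |
|---|---|---|---|
| 10% per arm, no gain kept | 0.535 | 0.594 | 0.595 |
| 10% per arm, half kept | 0.564 | 0.596 | 0.595 |
| 10% per arm, all kept | 0.600 | 0.601 | 0.601 |
| 20% vs 0%, no gain kept | 0.480 | 0.600 | 0.599 |

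Imputation yields an estimate for all 120. Without exposure information or off-training CRF values, that estimate is the completer contrast. The simulated ratios agree with the formula: 0.595/0.535 = 1.11 and 0.599/0.480 = 1.25.

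The distortion of the Aim 3 paths was not quantified.

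**The case against.** The strongest reply is that the procedure is silent on the test rather than prohibiting it, and that sections 6 and 18 plan post-training tests in general. Leaving the test out may also be deliberate: it is the most demanding assessment, section 18 lists cardiac risks for it, and section 13 is built to reduce burden. The numbers are small, and section 13 expects fewer losses than planned. Participants who attend poorly but stay enrolled can still have their scheduled test, and recorded attendance and heart-rate adherence could inform an imputation model. Because the mediation is labelled secondary and the fidelity check uses separate regressions, it is arguable whether the sentence about the main analysis covers them.

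Most of this limits the size of the point rather than removing it. Aim 3 is the CRF aim, and the intent-to-treat sentence names all three aims. The imputation that could use attendance is not written down.

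A reader might infer more than the documents support:

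- **That the CRF analyses cannot be intent-to-treat.** They can: participants can be kept in their assigned arm with CRF imputed. The difficulty is that the result would rest on an assumption with no requested off-training CRF to inform it.
- **That CRF is excluded by rule for drop-outs.** It is not requested, which is different.
- **That 15% drop-out is the plan's figure.** It is not; 5 points of that allowance are scanner motion.
- **That asking for the test at the listed steps would settle the matter.** Post-testing at drop-out captures fitness at that time, not at month 6, so the timing also has to be resolved.

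**Conclusion.** The point holds as a gap in data collection and in specification. CRF is not requested from drop-outs at any step, and no missing-data method is stated for the two analyses that need it. Followed as written, CRF would go unobserved for most of about 12 participants, possibly fewer.

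At the planned 10% drop-out in each arm, the overstatement of the CRF contrast lies between 0% and about 11%, with about 5% if half the gain is kept. It reaches 25% only if all 12 drop-outs are in the moderate arm and keep none of their gain. These figures assume no CRF change in the light arm and either a completer analysis or imputation that ignores exposure. The true retention of gain and the split by arm are unknown.

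The omission does not affect the primary connectivity analysis, because the first step seeks the MRI. The change is worth making because it is cheap and the missing measurement cannot be recovered afterwards, not because the trial's main result is in doubt.

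**What to change.** **Protocol section 13.** After MRI and cognitive testing have been requested, add a separate request for the already planned post-training VO2 test, subject to the physician screening the protocol already has. Keep it separate so that someone who declines it is not moved to a lower step and lost to the MRI. Record the test date. State how post-testing at drop-out relates to the 6-month terminus used in the analysis, since the two passages must be reconciled.

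**SAP section 17.** State that missing CRF in the fidelity and Aim 3 models will be multiply imputed using arm, baseline CRF, time of drop-out, percentage of sessions completed, percentage of sessions in the prescribed heart-rate zone, and observed connectivity and learning. A simple off-training indicator would rest on about 6 drop-outs per arm, so the exposure variables are the better basis. Extend the planned pattern-mixture sensitivity analysis to CRF, including a scenario in which moderate-arm drop-outs keep none of their gain.

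**Cost.** A sentence or two in the drop-out procedure, a short SAP addition and a little more analysis work. The test is already planned for each participant, so no new procedure is introduced. It does mean one more visit to request, which some drop-outs will decline or will not be cleared for. The sensitivity analysis is therefore needed in any case.
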